### **13.5.10.3 PGIC and CGI-I**

Both patients' (PGIC) and clinician's (CGI-I) global impression of improvement scales will be summarized at Weeks 18 and 76. Summaries will include the count and proportion of subjects at each point on the Likert scale as well as an 8-point descriptive summary. At Week 18, a t-test will be used to derive a p-value on the mean score of the placebo and tildacerfont groups.

### **13.5.10.4 Key Laboratory and Vital data used in Clinical Outcome Components**

Key laboratory and vitals parameters that are used to build key clinical outcomes will be summarized by treatment and post-baseline scheduled time point, based on randomized treatment received at each scheduled time point and will include p-values reporting change from baseline using paired-tests and difference from placebo using Wilcoxon rank sum tests.

- Fasting glucose, HbA1c, and fasting insulin
- Total cholesterol, LDL, HDL, triglycerides
- Blood pressure (systolic and diastolic)

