### **5.2.5 Efficacy Assessments**

Serum A4 collected at clinic visits for this study.

Additional efficacy assessments collected at clinic visits in Part A of the Treatment Period and/or the optional Open-Label Extension Period include:

- Serum 17-hydroxyprogesterone (17-OHP)
- Lesion volume of testicular adrenal rest tumors (TARTs) assessed by complete scrotal ultrasounds in male subjects
- Quality of life assessments (Short Form-36 [SF-36] total score)
- Acne assessments (Investigator's Global Assessment [IGA] of acne severity score)
- Hirsutism assessments (modified Ferriman Gallwey [mFG] score for hirsutism)
- Total daily dose of GC regimen(s)
- Cardiovascular risk factors, as collected by metabolic assessments

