## 10 STATISTICAL AND ANALYSIS ISSUES

### 10.1 Adjustments for Covariates

The categorical, randomization stratification variable (i.e., Week 4 A4 value [0 =  $A4 \leq 4 \times ULN$ ; 1 =  $A4 > 4 \times ULN$ ]) will be used in all efficacy analyses. The categorical variables treatment group (0 = placebo, 50 = 50 mg QD tildacerfont, 100 = 100 mg QD tildacerfont, and 200 = 200 mg QD tildacerfont) and sex (0=male, 1=female) will also be included efficacy analyses.

The log baseline serum A4, as a continuous covariate, will be included in a model for the analysis of change from baseline in A4 without the randomization stratification variable. The baseline GC dose, as a continuous covariate, will be included in models for the analysis of serum A4 and the change from baseline in GCs. The baseline value of continuous efficacy endpoints will be included in statistical models, such analysis of covariance (ANCOVA) or mixed-model for repeated measures (MMRM) as a continuous covariate for exploratory endpoints.

When fitting a logistic regression model, the treatment will be coded as 0 = placebo, 50 = 50 mg QD tildacerfont, 100 = 100 mg QD tildacerfont, and 200 = 200 mg QD tildacerfont. The treatment will be an explanatory variable in the model.

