#### **13.5.6.1 Statistical Modeling and Testing**

If the distribution of residuals is judged non-normal, this analysis will be accompanied by a rank-based ANCOVA model. Statistical testing will be performed using a (rank-based, if non-normal residuals) ANCOVA model. In general, the model will comprise the (rank of, if non-normal residuals) change from baseline value to study Week 18 as the dependent variable; randomized treatment group (0 = placebo, 50 = 50 mg QD tildacerfont, 100 = 100 mg QD tildacerfont, and 200 = 200 mg QD tildacerfont) and sex (0=male, 1=female) as fixed effects; baseline SF-36 total score and baseline GC dose as continuous covariates; the randomization stratum (0 =  $A4 \leq 4 \times ULN$ , 1 =  $A4 > 4 \times ULN$ ) as categorical explanatory variables. The estimation method for the ANCOVA model will REML. A significance level of 0.05 2-sided will be applied.

The ranked value is obtained by ranking all non-missing change from baseline values at the specified analysis visit, if a rank-based model is used.

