## **14 SAFETY ANALYSES**

Safety will be evaluated by AEs, SAEs, AESIs, clinical laboratory, vital signs (excluding the efficacy variables), ECG findings, monitoring for suicide risk and depression/anxiety, as well as physical examination. All analyses of the safety data will be performed using the safety analysis set, based on the actual treatment a subject received. Subjects who received different doses of study drug (placebo or tildacerfont) during the study will be assigned to the treatment group from the time when tildacerfont was received. All descriptive statistics (described in [Section 9.1](#)) will be presented by treatment group (including dose level) and treatment period.

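### The placebo comparisons of glucose, HbA1c, insulin, lipids and blood pressure (SAP 13.5.10.4) use a rank-sum test with no baseline adjustment, no stated analysis variable and no between-arm estimate or CI

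*SAP*

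**What the plan says.** SAP 13.5.10.4 is one of the additional exploratory analyses in the Efficacy chapter. It summarises fasting glucose, HbA1c, fasting insulin, the four lipids and blood pressure by treatment and post-baseline time point, and adds "p-values reporting change from baseline using paired-tests and difference from placebo using Wilcoxon rank sum tests". It names no covariate, stratification factor, between-arm estimate or interval. It does not say which variable the rank-sum test is applied to.

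SAP 5.2.5 lists "Cardiovascular risk factors, as collected by metabolic assessments" among the efficacy assessments, and SAP 5.2.5.6 defines those assessments to include the measures above.

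SAP 10.1 says the Week 4 A4 stratum "will be used in all efficacy analyses" and that "sex (0=male, 1=female) will also be included efficacy analyses". It also puts the baseline value of a continuous efficacy endpoint into models such as ANCOVA or MMRM for exploratory endpoints.

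For SF-36 change at Week 18, SAP 13.5.6.1 fits an ANCOVA with treatment, sex and stratum, plus "baseline SF-36 total score and baseline GC dose as continuous covariates", and a rank-based version if residuals are non-normal. SAP 13.5.6.2 reports LS-mean differences from placebo with SEs, 95% CIs and p-values.

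**The concern.** Part A is the only period with a placebo arm; at Week 18 the placebo subjects move to tildacerfont. With a planned 18 subjects per arm, a comparison of these measures with placebo needs what precision it can get. A pre-treatment value of each measure is collected on every subject. A two-sample rank-sum test cannot use that value as a covariate, so it gives up power and leaves any chance baseline imbalance only partly handled (if changes are ranked) or not handled (if raw values are).

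A p-value alone also does not tell a reader how large a metabolic difference from placebo is compatible with the data. In small arms with nominal testing, that is the more useful result.

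Finally, the section asks for a difference from placebo at every post-baseline time point, although no concurrent placebo group exists after Week 18.

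**Working it through.** **Inputs.** Arm size: Protocol 9.2 gives 15 per group and 15% dropout. 15/(1 - 0.15) = 17.6, so 18 per group, and 4 x 18 = 72, which reproduces the plan's total. That sizing is for A4; the plan states no power, SD or correlation for the metabolic measures. Two-sided alpha is 0.05 (SAP 9.2). The baseline-to-follow-up correlation r is my assumption, 0.5 to 0.9.

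**Variance of the between-arm difference**, in units of 2 x SD^2 / n, with equal SD at both visits:
- raw follow-up value: 1
- change from baseline: 2(1 - r)
- ANCOVA with own baseline: 1 - r^2

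For normal data the rank-sum test has efficiency 3/pi = 0.955 relative to the t-test. The variance of ANCOVA relative to each rank-sum version is therefore:
- against rank-sum on change: 0.955(1 - r^2)/[2(1 - r)] = 0.955(1 + r)/2
- against rank-sum on raw values: 0.955(1 - r^2)

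**Power of the rank-sum test for an effect ANCOVA detects with 80% power:** Phi(2.80 x sqrt(ratio) - 1.96), where 2.80 = 1.96 + 0.84. Arm size cancels. Example, r = 0.7 on change: ratio 0.955 x 0.85 = 0.81; 2.80 x 0.901 - 1.96 = 0.56; Phi(0.56) = 71%.

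| r (assumed) | Ratio, change | Power, change | Ratio, raw | Power, raw |
|---|---|---|---|---|
| 0.5 | 0.72 | 66% | 0.72 | 66% |
| 0.7 | 0.81 | 71% | 0.49 | 50% |
| 0.8 | 0.86 | 74% | 0.34 | 38% |
| 0.9 | 0.91 | 76% | 0.18 | 22% |

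**Simulation, normal data, 18 v 18** (6,000 runs per setting, one binary stratum in the ANCOVA), r = 0.5 / 0.7 / 0.9:
- ANCOVA: 78 / 78 / 76%
- rank-sum on change: 65 / 71 / 75%
- rank-sum on raw values: 66 / 49 / 20%

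Size was about 5% for all three.

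**Simulation, skewed (lognormal) data, 18 v 18** (4,000 runs), r = 0.5 / 0.7 / 0.8 on the log scale:
- ANCOVA on the log scale with log baseline: 76 / 76 / 77%
- rank-based ANCOVA with baseline, sex and stratum: 63 / 64 / 66%
- rank-sum on untransformed change: 48 / 54 / 58%
- rank-sum on raw values: 60 / 44 / 33%

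Skewness therefore does not justify leaving baseline out.

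**Sex and stratum.** In simulations where the stratum was not prognostic and sex acted only through baseline, adding both to a model that already had baseline gave no gain and cost about 2 to 4 points. A further run with both non-prognostic, r = 0.5 / 0.7 / 0.9, gave 74 / 72 / 73% for the full model, 76 / 76 / 76% for baseline only and 63 / 67 / 73% for rank-sum on change.

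**The case against.** The strongest reply is that this is a nominal, additional exploratory summary. The measures are not separate endpoints in SAP Table 1, and the nearest one, cardiovascular risk at the end of the open-label extension, is outside this SAP. Protocol 9.4.6.4 and 9.4.6.5 had already planned unadjusted t-tests for laboratory and vital-sign data under safety. That limits the importance and stands.

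A reader might infer several stronger points. The documents do not support them:

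- *The test ignores baseline.* Not established. The ranked variable is not stated, and ranking changes is a natural reading given the wording about change in the same sentence. Baseline would then be subtracted, though not adjusted for, and the loss is moderate to negligible. The low figures (50% down to about 20%) belong only to the raw-value reading.
- *Leaving out sex and the stratum loses precision.* Not shown; see the last calculation above. It is also not a clear breach on the stratum. SAP 10.1 itself describes an A4 model without it, and the primary model (13.3.2) and the A4 responder model (13.5.1.2) both omit it. The own-baseline sentence in 10.1 concerns statistical models, which a rank-sum test is not.
- *No effect size at all.* Arm-level means, SDs, medians and quartiles are planned (SAP 9.1). What is missing is a between-arm estimate with a CI.
- *The same criticism reaches the Week 18 PGIC and CGI-I comparison*, where "a t-test will be used to derive a p-value on the mean score of the placebo and tildacerfont groups". Those scales have no baseline score to adjust for, and SAP 15 notes that they are not named as efficacy assessments in the protocol synopsis or objectives.

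Rank-based ANCOVA also does not by itself fill the gap. A difference in mean ranks is not in mg/dL or mmHg.

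**Conclusion.** The point holds as a minor one. The placebo comparison in SAP 13.5.10.4 is unadjusted for own baseline, its analysis variable is undefined, and it yields no between-arm estimate or interval, while the SAP already does better for SF-36 at the same visit.

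If changes are ranked, the power loss against baseline-adjusted ANCOVA is about 13 points at r = 0.5 (78% to 65%), shrinking to almost nothing at r = 0.9. If raw values are ranked, it is about 12 points at 0.5 and more than 50 at 0.9 (76% to 20%). These sizes rest on assumed correlations, equal variances at both visits, 18 evaluable subjects per arm and, for the main figures, normal data. No primary, secondary or numbered exploratory conclusion depends on this analysis.

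**What to change.** In SAP 13.5.10.4:

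1. Restrict the placebo comparison to Part A visits: Week 18 for fasting glucose, insulin and HbA1c; Weeks 10, 14 and 18 for lipids and blood pressure, following the schedule of assessments. Keep later visits descriptive against baseline.
2. Replace the rank-sum test with ANCOVA on change from baseline, with randomised treatment and the parameter's own baseline.
3. Include sex, the Week 4 A4 stratum and baseline GC dose for consistency with 10.1 and 13.5.6.1, not as a claimed gain in precision.
4. Analyse skewed measures such as insulin and triglycerides on the log scale with log baseline, and back-transform to a ratio to placebo, as the SAP already does for A4.
5. Report each dose against placebo as a difference or ratio with 95% CI. Keep rank-based ANCOVA as a supportive p-value only.
6. Record in SAP 15 the departure from the t-tests in Protocol 9.4.6.4 and 9.4.6.5, which is not listed there now.

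The cost is SAP wording and programming; every covariate is already collected. If the sponsor prefers to keep the rank-sum test, the minimum is to name the ranked variable, add a between-arm estimate with CI, and state that 10.1 does not apply here.

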## **14 SAFETY ANALYSES**

Safety will be evaluated by AEs, SAEs, AESIs, clinical laboratory, vital signs (excluding the efficacy variables), ECG findings, monitoring for suicide risk and depression/anxiety, as well as physical examination. All analyses of the safety data will be performed using the safety analysis set, based on the actual treatment a subject received. Subjects who received different doses of study drug (placebo or tildacerfont) during the study will be assigned to the treatment group from the time when tildacerfont was received. All descriptive statistics (described in [Section 9.1](#)) will be presented by treatment group (including dose level) and treatment period.

#### **14.1 Adverse Events**

All AE verbatim terms reported on the eCRFs will be coded using the Medical Dictionary for Regulatory Activities (MedDRA® version 23.0).

All reported AEs (including non-TEAEs) will be listed. Separate listings will be provided for SAEs, AESIs, and TEAEs leading to study drug discontinuation. For all TEAE tables, counting will be by subject and not by event. Additionally, if a subject reported the same TEAE on multiple occasions, the highest severity (severe > moderate > mild) or study drug relationship (related > probable > possible > unlikely > unrelated) recorded for the event will be summarized. All TEAE summary tables will present the number and percentages of subjects reporting TEAEs, unless otherwise specified. A summary of TEAEs by severity, seriousness, and relation to study drug will be tabulated.

AEs experienced during the Run-in Period will be reported separately. For Part A, AEs will be summarized by the actual randomized dose. For Part B, AEs will be summarized under the treatment at the onset of the AE. A subject who does-escalates in Part B will be counted within the denominator of each treatment group that s/he received. For example, a subject who started at 50 mg of tildacerfont, escalated to 100 mg of tildacerfont, and escalated again to 200 mg tildacerfont will be counted in all three dose levels; the AE that the subject experiences will be counted once under the dose level that the subject was taking at the onset of the AE. For Part C, all subjects will receive 200 mg tildacerfont.

An overall summary of AEs will be presented by study period (i.e., Part A, Part B, and Part C). The overall summary will include the number and percentage of subjects experiencing any AEs, study drug related AEs, AEs by maximum severity (highest toxicity grade), SAEs, study drug related SAEs, discontinued due to AE, and deaths.

The number and percentage of subjects experiencing each AE, study drug related AE, and SAEs will be summarized by treatment group according to system organ class and preferred term.

Additional table including only preferred term summarized by treatment for the number and percentage of subjects experiencing each AE will be presented as well

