6.1.2 Treatment Assignment, Dosing, and Administration

Subjects will use their own physician-prescribed supply of GCs as prescribed during the study, including during the Run-in Period.

Subjects will take placebo (during the Run-in Period) or assigned study drug (during the Treatment Period) orally each day between 6 PM and midnight, with an evening meal. The evening meal should contain approximately 25-50% fat content. Study drug may be consumed up to 30 minutes after completing the evening meal, if necessary.

During Part A (the first 12 weeks of the Treatment Period), subjects will be randomized in a 1:1:1:1 ratio to receive either placebo or tildacerfont at a dose of 50 mg QD, 100 mg QD, or 200 mg QD.

During Part B (the second 12 weeks of the Treatment Period) and Part C (the last 46 weeks of the Treatment Period), all subjects will receive active drug (tildacerfont).

- Subjects who were randomized to placebo in Part A will receive tildacerfont 100 mg QD at the beginning of Part B.
- Subjects who were randomized to tildacerfont 200 mg QD in Part A will continue to receive tildacerfont at 200 mg QD throughout Parts B and C.
- Based on A4 results from the Weeks 18 and 24 study visits, eligible subjects may undergo a tildacerfont dose escalation after each of these study visits. Specifically:
 - Subjects taking tildacerfont 50 mg QD will either continue to receive the same dose (if A4 ≤ULN) or be escalated to tildacerfont 100 mg QD (if A4 >ULN and the subject is tolerating his/her current tildacerfont dose)
 - Subjects taking tildacerfont 100 mg QD will either continue to receive the same dose (if A4 ≤ULN) or be escalated to tildacerfont 200 mg QD (if A4 >ULN and the subject is tolerating his/her current tildacerfont dose).
- At Week 30, all subjects will be escalated to 200 mg QD.

Immediately following the Weeks 18 and 24 visits, subjects will continue to take their previously assigned study drug until A4 laboratory results are received, the RTSM system determines the appropriate tildacerfont doses for the next portion of the study, and subjects receive their tildacerfont doses for the next portion of the study. Subjects will receive enough previously assigned study drug to last until they receive their appropriate tildacerfont dose for the next portion of the study. Subjects will either return to the clinic to pick up their study drug or will be shipped their study drug.

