9.2 Sample Size Determination

A sample size of n=15 subjects per group will provide at least 80% power to detect a difference of at least 50% in A4 mean percent change from baseline between a given dose level of tildacerfont and placebo, assuming a common SD of 30%.

An assumed dropout rate of 15% during the Treatment Period results in a target of 18 subjects per group and a total sample size of 72 subjects who enter the Treatment Period.

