### **9.1 Presentation of Summary Statistics**

For most summary statistics, data will be analyzed and displayed in tabular format.

Unless otherwise specified, continuous serum hormones (A4, 17-OHP, ACTH) will be summarized using a 11-point descriptive statistics (i.e., n, mean, standard deviation [SD], median, 25% quartile [Q1], 75% quartile [Q3], minimum, maximum, geometric mean, geometric coefficient of variance [CV%], 95% confidence interval [CI] for geometric mean [including geometric mean ratio and its 95% CI]).

All other continuous variables will be summarized using an 8-point descriptive summary (n, mean, SD, median, Q1, Q3, minimum, and maximum) unless otherwise specified.

The same number of decimal places as in the observed value will be presented when reporting minimum and maximum; 1 additional decimal place than in the observed value will be presented when reporting mean, median, Q1, Q3, geometric mean, 95% CI; 2 additional decimal places than in the observed value will be presented when reporting SD. Geometric CV% will be reported to one decimal place. All percentages will be presented to 1 decimal place, unless otherwise specified.

All categorical/qualitative data will be presented using the frequency of events and percentages. Percentages equal to 100 will be presented as 100% and percentages will not be presented for zero frequencies. For summaries of AEs and concomitant medications (CMs), the percentages will be based on the number of subjects who received the study drug dose within the period that is being summarized.

All analyses and summaries will be produced using SAS® version 9.4 or higher.

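### Part B adverse-event percentages by dose are not comparable across columns, because time at each dose differs by design and an escalating subject counts in full in every dose denominator

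*SAP*

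**What the plan says.** SAP 14.1 sets the statistic: "All TEAE summary tables will present the number and percentages of subjects reporting TEAEs, unless otherwise specified". SAP 9.1 sets the general denominator for adverse events: "the percentages will be based on the number of subjects who received the study drug dose within the period that is being summarized".

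For Part B, SAP 14.1 adds two rules. On the denominator: "A subject who does-escalates in Part B will be counted within the denominator of each treatment group that s/he received". On the numerator, an event "will be counted once under the dose level that the subject was taking at the onset of the AE". Its example is a subject who moves from 50 to 100 to 200 mg and appears in all three columns. SAP 14.1.1 and 14.1.2 apply this layout, by study period and dose level, to the overall summary, SAEs, AESIs and events leading to discontinuation.

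No person-time denominator, exposure-adjusted rate or minimum time at a dose is specified. SAP 12.1 summarises duration of exposure by dose level, but separately from the event counts.

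On dosing, Protocol 6.1.2 allows escalation after Weeks 18 and 24 when A4 is above ULN and the subject tolerates the current dose. After each of these visits, "subjects will continue to take their previously assigned study drug until A4 laboratory results are received" and the new supply arrives. The length of that wait is not given.

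**The concern.** A subject randomised to 200 mg spends the whole of Part B in one column. A subject who escalates divides the same 12 weeks among two or three columns and still adds one to each denominator. A crude percentage rises with time observed, so columns with different mean times at dose will differ even when dose has no effect on adverse events.

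The study is meant to help identify a dose (Protocol 4.2 and 4.3). Everyone is on 200 mg in Part C, so Part B holds the only by-dose safety table after the placebo-controlled phase. Readers will compare its columns, and nothing beside the percentages will show how much of a difference is exposure time.

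**Working it through.** **The plan's own figure.** Protocol 9.2 gives 15 per group and 15% dropout: 15 / 0.85 = 17.6, rounded up to 18, and 4 × 18 = 72. This reproduces "a target of 18 subjects per group and a total sample size of 72 subjects who enter the Treatment Period". The documents state no adverse-event rate and no dose-specific exposure.

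**Inputs from the documents.** 18 per arm; Part B runs from Week 18 to Week 30; former placebo subjects start Part B at 100 mg; escalation as in Protocol 6.1.2.

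**Assumptions.**
- The hazard h is the same at every dose, with 50% having an event over 12 weeks: h = ln 2 / 12 per week. A stay of w weeks then shows 1 − exp(−hw): 5.61% for 1 week, 25.08% for 5, 29.29% for 6, 33.26% for 7, 47.03% for 11 and 50% for 12.
- The wait on the old dose is 1 week (0 to 2 weeks also tried).
- The probability q of A4 above ULN at each escalation visit is 0.6 (0.2 to 0.8 also tried). Protocol 2.3.2 reports 40% normalisation in a study of another dose; nothing is given for this one.
- A4 status at Week 24 is independent of Week 18, or fully persistent.
- All subjects tolerate their dose, and dropout is ignored.

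Any difference between columns is then an artefact.

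**Reading 1: carried-over days belong to Part B** (wait 1 week, q = 0.6, independent).
- 50 mg, 18 subjects: 60% stay 1 week, 24% stay 7 weeks, 16% stay 12 weeks. 0.60 × 5.6126 + 0.24 × 33.258 + 0.16 × 50 = 3.3676 + 7.9819 + 8.0000 = 19.3495, reported as 19.3%. Mean stay 4.2 weeks.
- 100 mg, 51.12 subjects: 10.8 stay 1 week, 4.32 stay 5, 17.28 stay 6, 4.32 stay 7, 11.52 stay 11 and 2.88 stay 12. Expected subjects with an event: 15.05. 15.05 / 51.12 = 29.4%. Mean stay 6.4 weeks.
- 200 mg, 50.4 subjects: 18 stay 12 weeks, 10.8 stay 11 and 21.6 stay 5. (9.00 + 5.08 + 5.42) / 50.4 = 38.7%. Mean stay 8.8 weeks.

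The denominators add to 18 + 51.1 + 50.4 = 119.5 for 72 subjects.

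**Reading 2: carried-over days belong to Part A.** SAP 9.3.23.3 and Table 7 start Part B exposure at the first dose from the Week 18 dispensation and end Part A the day before. Subjects who leave 50 mg at Week 18 then never enter the Part B 50 mg column. For the 7.2 who remain: 0.6 × 29.29 + 0.4 × 47.03 = 36.4%.

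| Scenario (wait 1 week unless stated) | 50 mg | 100 mg | 200 mg |
|---|---|---|---|
| Reading 1, q = 0.2, independent | 38.4% | 40.1% | 43.4% |
| Reading 1, q = 0.6, independent | 19.3% | 29.4% | 38.7% |
| Reading 1, q = 0.8, independent | 11.8% | 25.3% | 37.6% |
| Reading 2, q = 0.6, independent | 36.4% | 35.2% | 37.6% |
| Reading 2, q = 0.6, persistent | 47.0% | 36.4% | 37.6% |
| Reading 2, q = 0.4, independent, wait 2 weeks | 38.0% | 36.2% | 35.4% |

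With a wait of 1 or 2 weeks there are 16 scenarios per reading. Under Reading 1, both lower doses fall below 200 mg in 15 of 16. Under Reading 2 this happens in 3 of 16, and both lie above 200 mg in 8. With 20% incidence over 12 weeks in place of 50%, Reading 1 at q = 0.6 (independent) gives 7.2%, 11.0% and 14.9%, still about a twofold spread.

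**The two SAP texts.** Escalation can follow only Weeks 18 and 24. A subject can therefore be in three dose columns within Part B only if the carried-over 50 mg days count as Part B, which is Reading 1. The Table 7 boundary gives Reading 2. The SAP does not say which governs the adverse-event tables.

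**Effect of a person-time rate.** Under the same model every column, on either reading, returns ln 2 / 12 × 52 × 100 = about 300 first events per 100 person-years.

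**The case against.** A reader might infer that the table is bound to make the low doses look safer than 200 mg. The documents do not support that. The direction depends on which period owns the carried-over days, on how many subjects escalate and on whether A4 status persists. The 200 mg column is diluted as well, by subjects who reach it after Week 24 and have 6 weeks or less there. Escalation also requires tolerating the current dose, which selects tolerant subjects into higher doses and works against a trend towards 200 mg.

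A reader might also set a one-week stay (5.6%) against a 12-week stay (50%). Those are single stays; no column consists only of one or the other. The column-level contrast in the Reading 1 case above is about twofold.

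The case for leaving the plan alone is that Part A already gives a randomised, double-blind, 12-week comparison by dose without escalation, that Part B tables are descriptive with no decision attached, and that SAP 12.1 shows exposure by dose elsewhere. This stands, and it limits the importance of the point. It does not make the Part B columns comparable, and a separate exposure table does not let a reader adjust a percentage.

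A person-time rate is also no full cure. It removes the artefact exactly only under a constant hazard. It does not address selection by A4 and tolerability, or residual drug from the previous dose (half-life about 60 hours, Protocol 4.3). Rates for rare terms will be imprecise with 18 per arm. These limits call for a footnote; they do not justify omitting the rate.

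**Conclusion.** The point holds as one about comparability. The planned Part B percentages mix dose with time at dose, and under equal true hazard they can show a spread of about 19% to 39% across doses when carried-over days count as Part B. When those days count as Part A, the spread is small or can reverse, so no direction of bias should be claimed. The sizes rest on an assumed hazard, wait and escalation probability, none of which the documents give for this study. The structural facts (crude percentages, full counting in each column, no exposure adjustment) come directly from the SAP. Since Part A carries the dose comparison, this is an inexpensive improvement to reporting and does not threaten the study's conclusions.

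**What to change.** 1. In the Part B by-dose TEAE tables (at least the overall summary, SAEs, AESIs and events leading to discontinuation), add exposure-adjusted incidence beside the crude percentages: subjects with a first event at a dose, divided by person-time at risk on that dose, with a 95% CI.
2. Reconcile the three-dose example in SAP 14.1 with the period boundary in SAP 9.3.23.3 and Table 7, and state which period owns the days on carried-over drug in the adverse-event tables.
3. Footnote these tables: escalation depends on A4 above ULN and on tolerating the current dose, so dose comparisons should rest on Part A.

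The cost is slightly more programming and extra columns in a few tables; first-dose dates and exposure durations by dose are already planned. The drawback is imprecise rates for rare terms, which the intervals will show.
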